5.3. Participant Stipends and Payments

Participants will be paid \$50 for all visits that do not involve skin biopsy (Screening and visits 3, 4, 5, and 7) and \$150 for the three visits that involve skin biopsy (baseline, visit 2, and visit 6), for a total of \$700. Other contacts are not reimbursed. For those subjects traveling >200 miles to OHSU, travel will be reimbursed at the federal Internal Revenue Service suggested rate of \$0.545/mile up to 1000 miles (range \$218 - \$1090 for a round-trip visit to OHSU) for each of the three in-person visits (baseline, visit 2, and visit 6).

Visit	Pre- trial	Screening*	Enrollment	V1	V2	V3	V4	V5	V6	V7
Week				WK0	WK4	WK8*	WK12*	WK20*	WK24	WK36*
Baseline Documentation										
Confirmation of dx	Х									
Informed consent		Х								
Investigator assessment		Х		Х	х	х	х	х	х	х
Medical history		Х		Х	Х	Х	Х	Х	Х	Х
Exclusion/Inclusion criteria		х	Х							
Dosing										
Injection counseling/training				Х						
Injection review					Х		Х	Х		
Study drug dispensing				х	х					
Study drug injection/dose**				х	х		х	х		
Laboratory Studies										
Blood draw***		Х		Х	Х		Х		Х	
Other Assessments and Procedures										
Skin biopsy				Х	Х				Х	
Adverse events				Х	Х	Х	Х	Х	Х	Х
Subject REDCap survey				Х	Х	Х	Х	Х	Х	х

5.4. Table 1: Study Schedule of Events

*Visit optionally to be performed via secure telemedicine videoconferencing for subjects >30 miles from Oregon Health & Science University. ***Guselkumab subcutaneous dose: 100mg on W0, W4, W12, W20. ****Laboratory studies will include: CBC and CMP at screening, W4, W12, and W20 as well as HBV, HCV, HIV, tuberculosis, and pregnancy (for females if childbearing potential) at screening.

6. INVESTIGATIONAL PRODUCT AND TREATMENT PLAN

6.1. Investigational Product: Guselkumab

Guselkumab is a humanized monoclonal antibody that binds and blocks IL-23.

6.2. Dosing and Administration

Guselkumab treatment will be administered at the FDA-approved dosing schedule for psoriasis as follows:

• 100 mg SC injection at week-0, week-4, week-12, and week-20

The 1 mL single-dose pre-filled syringe will be injected at room temperature into the subcutaneous tissue of the upper arms, thighs, or abdomen, avoiding areas affected by PRP when possible. Each injection will be administered in an anatomic location different from the previous injection, and the location will be recorded. Injections will be performed by qualified study personnel or by the subject after proper training in SC injection technique. Injections performed at home by the subject will be recorded by the subject in an injection diary and returned to the investigators.

6.3. Storage

The study drug will be stored in the Research Pharmacy and all applicable Research Pharmacy policies and procedures will be followed.

6.4. Concomitant Medications, Treatments, and Procedures

6.4.1. Concomitant Medication Recording

All concomitant medications taken during the study must be recorded. Subjects will be asked about concomitant medications at each study visit.

6.4.2. Prohibited Medications, Treatments, and Procedures

The following therapies will not be permitted during the course of the study:

- Treatment with systemic therapy intended to treat PRP within the washout period specified in the exclusion criteria, including prednisone, methotrexate, cyclosporine, acitretin, and injectable biologic therapies. These medications could have a negative safety impact on the subjects enrolled and confound the results of the study.
- New use of topical steroids or increased potency of topical steroids after enrollment
- Live vaccines
- Phototherapy within the 4-week washout period

6.4.3. Permitted Medications, Treatments, and Procedures

The following medications will be permitted during the course of the study:

- Topical emollients
- Topical steroids may be maintained at levels used prior to enrollment, decreased, or discontinued, but potency and weekly grams used may not be increased
- Non-live vaccines (such as the non-live annual influenza vaccine, non-live herpes zoster vaccine (Shingrix), rabies, or tetanus) and/or emergency vaccines are allowed
- Acetaminophen, aspirin, or ibuprofen as needed
- Subjects will maintain their usual medication regimen for other concomitant diseases throughout
 the study unless specifically excluded in the protocol. Subjects taking concomitant medications
 should be on a stable dose throughout the study, unless changes need to be made for an AE or
 for appropriate medical management. If a medication is changed, the changed and reason for it
 will be documented. Additional systemic drugs are to be avoided during the study, unless

required to treat an AE. Other medications may be allowed, if approved by the investigator. Any changes in medications should be discussed with the investigator. Subjects should be instructed to consult the investigator or other appropriate study personnel at the site before taking any new medications or supplements. All therapies (prescription, over-the-counter, vitamins, herbal supplements, vaccines) will be recorded in the eCRF as outlined in the Study Procedures.

7. STATISTICAL CONSIDERATIONS

7.1. Sample Size Computation and Power Analysis

This is a pilot study with no published baseline data; thus a power analysis was performed with the following rough assumptions. With measurement of the mean paired difference in PASI score before and after treatment of a minimum of 10 subjects, we would have 80% power at the 0.05 level to detect a mean within-subject change of 8-points when the standard deviation is 8-points. Due to the uncertainty inherent with a pilot study, the goal number of subjects with PRP who will be recruited for the study is 15.

				Mean Change	Standard
Power (1-ß)	Sample Size	а	ß	in PASI	Deviation
0.9998	10	0.05	0.0002	-8	4
0.9940	10	0.05	0.0060	-8	5
0.9621	10	0.05	0.0379	-8	6
0.8942	10	0.05	0.1058	-8	7
0.8031	10	0.05	0.1969	-8	8
0.9873	10	0.05	0.0127	-6	4
0.9203	10	0.05	0.0797	-6	5
0.8031	10	0.05	0.1969	-6	6
0.6755	10	0.05	0.3245	-6	7
0.5620	10	0.05	0.4380	-6	8

7.2. Statistical Analysis Plan

Data analysis will be ongoing throughout the trial by the PI and is expected to be complete within 3 months after the last-subject last-visit.

7.2.1. Primary Endpoint Analysis

• Mean improvement from baseline PASI at week-24 will be analyzed for statistical significance using a paired, two-tailed Student's t-test.

7.2.2. Secondary Endpoint Analyses:

- Time (weeks) to improvement by 50% in the PASI score (PASI 50) will be reported as a mean with standard deviation and also represented graphically.
- Mean improvement from baseline BSA at week-24 will be analyzed for statistical significance using a paired, two-tailed Student's t-test.
- The proportion of subjects achieving a Physician's Global Assessment of 0 or 1 at week-24 will be reported as a proportion, and compared with historical estimates of treatment success with acitretin and methotrexate (1).
- The proportion of subjects achieving a Palmoplantar Physician's Global Assessment of 0 or 1 at week-24 will be reported as a proportion.
- The mean improvement in nail involvement measured by NAPSI (see below) at week-24 will be analyzed for statistical significance using a paired, two-tailed Student's t-test.
- The proportion of subjects achieving a 4-point improvement in DLQI and the proportion of subjects achieving a DLQI score of 0 or 1 at week-24 will be reported as proportions. The mean

improvement in DLQI score from week-0 to week-24 will be analyzed using a paired, two-tailed Student's t-test.

• The mean improvement in PSSD at week-24 will be analyzed for statistical significance using a paired, two-tailed Student's t-test. The proportion of subjects achieving a PSSD of zero at week-24 will be reported as a proportion.

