There is no FDA-approved therapy for PRP, not a single published systematic therapeutic clinical trial, and no established guidelines for measuring disease severity. Commonly prescribed systemic medications include acitretin and methotrexate, but these have treatment failure rates of over 40% (1) and can be limited by side effects. Tumor necrosis factor inhibitors have been used for PRP but have even higher failure rates (1). While there are no published reports of IL-23p19 subunit-targeted therapy in PRP, there are case reports and case series of the use of IL-12/IL-23p40 subunit inhibition for PRP in over twenty patients (2, 9-23) with 90% of these showing marked improvement, often only 4 weeks after a single subcutaneous injection. For these reasons, guselkumab is proposed as a therapeutic intervention with potential for improving the lives of PRP patients.

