3.2.2. Secondary Endpoints Assessed by Investigator

- Time to improvement by 50% in the PASI score (PASI 50)
- Mean reduction in body surface area (BSA) at week-24. BSA is collected as part of the PASI assessment tool.
- Proportion of subjects achieving a Physician's Global Assessment (PGA) of 0 or 1 at week-24
- Proportion of subjects achieving a Palmoplantar Physician's Global Assessment (PPPGA) of 0 or 1 at week-24. Palmoplantar disease will be assessed separately from overall disease since it has high morbidity and may respond differently to therapy.
- Mean percentage improvement in nail involvement measured by Nail Psoriasis Severity Index (NAPSI) at week-24. The Nail Psoriasis Severity Index (NAPSI) (24) will be used for evaluating the fingernails and toenails of subjects with PRP. This is expected to be useful tool because nails in PRP have many overlapping features with psoriasis including nail plate crumbling, splinter hemorrhages, nail oil drop (yellow-brown) discoloration, and nail bed hyperkeratosis, although PRP nails are less likely to have onycholysis and red spots in the lunula (25).

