3.2.3. Secondary Endpoints Assessed by Subject

 Proportion of subjects achieving a 4-point improvement in quality of life measured by the Dermatology Life Quality Index (DLQI) at week-24, proportion of patients achieving a DLQI of 0 or 1 at week-24, and mean improvement in DLQI score at week-24. The DLQI (26) is a validated tool for inflammatory skin conditions. It is a 10-question survey, scored 0 – 30 points. For inflammatory skin conditions, a 4-point change in DLQI score is considered clinically important (27).

- Mean percentage in improvement in Psoriasis Symptoms and Signs Diary (PSSD) at week-24, and proportion of patients achieving a PSSD of zero at week-24. The PSSD is an 11-question 0 – 10-point numeric rating scale (NRS) patient-reported outcome measure assessing itch, dryness, cracking, skin tightness, scaling, shedding or flaking, bleeding, burning, stinging, and pain over the last 24 hours and 7 days respectively (28).
- Mean change from baseline individual PRP Area and Severity Index (iPRPASI) at week-24 after treatment with guselkumab, and correlation of subject-assessed iPRPASI scores with investigator-assessed PASI scores. The IPRPASI is a novel subject self-assessment score of disease involvement and severity, based on a previously published similar tool validated for psoriasis (29).
- Sustained remission at week-36, 16 weeks after the last guselkumab dose, as measured by the mean change in PASI from week-24 to week-36. Sporadic PRP is often a self-limited disease, resolving spontaneously after an average of 3-6 years. Other immunomodulatory medications have induced sustained remission of PRP (22), so there is a potential that treatment may "reset" the immune response and lead to long-term improvement in the disease, especially in subjects without genetic mutations. Subjects will be treated with guselkumab as per the FDA-approved psoriasis treatment guidelines, and therapy will be stopped after the 20-week dose. Subjects will be monitored at 24 weeks (primary study endpoint) and then at 36 weeks to assess for sustained remission versus relapse.

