3.2.4. Exploratory/Mechanistic Endpoints

- Treatment response, as measured by PASI 50, stratified by the presence or absence of germline CARD14 mutations. Genetic CARD14 gain-of-function mutations were identified in 3 families with familial PRP as well as 12.5% of individuals with sporadic PRP (3). Genetic CARD14 mutations will be measured in study subjects and associated with treatment response to guselkumab. Additionally, de-identified samples will be stored indefinitely for future analysis of genes associated with PRP.
- Normalization of CARD14 epithelial expression at week-24. Despite the fact that not all patients with PRP have genetic CARD14 mutations, immunohistochemical staining of CARD14 in 6 of 6 biopsies from sporadic cases of PRP without germline genetic mutations showed increased expression of CARD14 in the keratinocyte spinous and granular layers of the epidermis (2). CARD14 is thought to act in a synergistic manner with IL-17, activating the transcription factor NF-kB. NF-kB activation was shown *in vitro* to stimulate IL-36gamma, which may induce an amplifying feedback loop from IL-23 to IL-17 and back again (6). Cutaneous biopsies will be obtained from subjects before and 24 weeks after treatment with guselkumab. Inhibition of IL-17 by guselkumab is expected to lead to normalization of CARD14 expression by keratinocytes.
- Normalization of cutaneous gene expression at weeks 4 and 24. Upregulation of Th17 cytokines (IL-17A, IL-17F, IL-22) and pro-inflammatory innate cytokines (TNF, IL-6, IL-12, IL-23, IL-1beta) compared to normal skin were observed in lesional skin from 3 subjects with PRP (5). In order to better understand the inflammatory pathways involved in PRP, lesional and non-lesional biopsies will be obtained from subjects at week-0 prior to the first dose of guselkumab, week-4, and week-24. Cutaneous gene expression of the epidermis and dermis will be analyzed by RNA Sequencing (RNA-Seq and therapeutic response to guselkumab is expected to correlate with normalization of epidermal cytokine levels. De-identified tissue samples will be stored indefinitely for analysis.
- Change in serum cytokine levels at weeks 4 and 24. Serum levels of multiple cytokines have been shown to correlate with disease activity in patients with psoriasis (*30*) but these have not been investigated in patients with PRP. Serum cytokine levels before and after treatment with guselkumab will be analyzed by multiplexed bead-based immunoassay.

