4. STUDY ENROLLMENT AND WITHDRAWAL

4.1. Inclusion criteria

- Diagnosis of PRP by clinical assessment and biopsy.
- Male subject age 18-99, willing to use a reliable form of birth control if sexually active with a woman who is able to become pregnant.
- Female subject age 18-99; either of non-childbearing potential or of childbearing potential who test negative for pregnancy and agree to use a reliable method of birth control or remain abstinent during the study and for at least 12 weeks following the last dose of guselkumab.
- Involved BSA ≥ 10% at baseline.
- Are a candidate for phototherapy and/or systemic therapy.
- Willingness to travel to OHSU for all study visits, or willing/able to participate in remote videoconferencing visits with access to a computer with internet capabilities and webcam.
- Have given written informed consent approved by the OHSU Investigational Review Board.

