7.2.3. Exploratory Endpoint Analyses

- Sustained remission at week-36, measured by the mean change in PASI score from week-24 to week-36, will be analyzed for statistical significance using a paired, two-tailed Student's t-test.
- Treatment response, as measured by PASI 50, will be stratified by CARD14 germline mutations. The proportion of subjects with a PASI 50 response with and without CARD14 mutations will be reported and compared for statistical significance using an unpaired, two-tailed Student's t-test.
- Epithelial expression of CARD14 will be assessed qualitatively by a trained dermatopathologist who is blinded to the biopsy collection time (before or after therapy).
- The gene expression level from the tissue biopsy, before, 4 weeks, and 24 weeks after treatment, will be analyzed for statistical significance using a pared, two-tailed Student's t-test and also compared with normal and psoriatic skin using a two-tailed, two-sample Student's t-test with unequal variance adjusted for multiple comparisons.
- The cytokine level from serum before, 4 weeks, and 24 weeks after treatment, will be analyzed for statistical significance using a pared, two-tailed Student's t-test and also compared with normal and psoriatic serum using a two-tailed, two-sample Student's t-test with unequal variance adjusted for multiple comparisons.

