8.7. Participant Discontinuation of Study Drug or Withdrawal from the Study

8.7.1. Participant Discontinuation of Study Drug

A subject who discontinues study drug administration will not be automatically withdrawn from the study if they discontinue study drug administrations before the end of the study drug administration period. If a subject discontinues study drug before week-24, the week-24 study visit will be performed early if the subject is willing and able to participate.

A subject's study drug must be discontinued if:

- The investigator believes that for safety reasons or tolerability reasons (e.g., AE) it is in the best interest of the subject to discontinue study drug
- The subject becomes pregnant or plans a pregnancy within the study period.
- The subject (or the subject's representative) withdraws consent for administration of study drug.
- The subject develops a systemic opportunistic infection.
- The subject is deemed ineligible according to the following TB screening criteria:
 - A diagnosis of active or latent TB is made.
 - A subject has symptoms suggestive of active TB based on follow-up assessment questions and physical examination, or has had recent close contact with a person with active TB, and cannot or will not continue to undergo additional evaluation.
- The subject develops an allergic reaction resulting in bronchospasm with wheezing or dyspnea that requires ventilatory support. In general, discontinuation of study drug administration must be considered for subjects who develop a severe allergic reaction.
- The subject has a reaction resulting in myalgia or arthralgia with fever or rash (suggestive of serum sickness and not representative of signs and symptoms of other recognized clinical syndromes) occurring 1 to 14 days after an injection of study drug. These may be accompanied by other events including pruritus, facial, hand, or lip edema, dysphagia, urticaria, sore throat, and headache.
- The subject has a malignancy, not including cutaneous squamous cell skin cancer < 2 cm in diameter or basal cell skin cancers that are adequately treated with no evidence of residual disease.
- The subject has any severe infection (NCI-CTCAE Grade 3 or higher) that is considered related to the study drug by the investigator.

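### Time to PASI 50 is summarised as a mean and SD with no horizon and no rule for subjects who never reach it; a lesser, exploratory point is the t-test of PASI 50 by CARD14 status.

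*Combined protocol and SAP*

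**What the plan says.** Time to PASI 50 is a secondary endpoint. Section 7.2.2 states: "Time (weeks) to improvement by 50% in the PASI score (PASI 50) will be reported as a mean with standard deviation and also represented graphically". The type of graph is not given. Section 3.2.2 attaches no week to this endpoint, although the BSA, PGA, PPPGA and NAPSI endpoints listed with it are all set at week 24. After baseline, PASI is scored at weeks 4, 8, 12, 20, 24 and 36.

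The protocol points to week 24 as the natural horizon without saying so. Under Section 3.2.3 "therapy will be stopped after the 20-week dose", and week 36 serves to separate remission from relapse. Section 8.7.1 adds: "If a subject discontinues study drug before week-24, the week-24 study visit will be performed early", and Section 8.7.2 does the same for subjects who withdraw. Section 7.2 contains no censoring, imputation or missing-data rule.

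For the exploratory item, Section 7.2.3 says that the proportions with a PASI 50 response "with and without CARD14 mutations will be reported and compared for statistical significance using an unpaired, two-tailed Student's t-test". No time point for that response is given. Section 3.2.4 reports that CARD14 "mutations were identified in 3 families with familial PRP as well as 12.5% of individuals with sporadic PRP". Entry under Section 4.1 requires "Diagnosis of PRP by clinical assessment and biopsy" and is not limited to sporadic disease.

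**The concern.** A mean and SD need a number from every subject. Someone who never halves the PASI has no such number, so either the subject drops out of the average or a value is chosen that the plan does not name. A responder-only mean says how quickly responders responded. It does not describe speed of response in the treated group, and it hides slow or absent response. Section 7.2 has the principal investigator analysing data throughout the trial, so a horizon or rule that is still open could be settled after results are visible.

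The CARD14 comparison is a 2x2 table with very few subjects in one group. A t-test there can return a small p-value on one carrier, and no usable p-value when there is no variation within either group.

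**Working it through.** **Plan's own figure.** The only design calculation is the power of the paired t-test on PASI change (Section 7.1). With n = 10, mean change 8, SD 8 and two-sided 0.05, the noncentral t gives 0.8031, as tabulated. It covers neither item here.

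**(a) How likely are non-responders?** The closest favourable response figure is in Section 1.1, "with 90% of these showing marked improvement, often only 4 weeks after a single subcutaneous injection". It comes from case reports of IL-12/23 p40 inhibition and is not PASI 50, so 90% is an assumption, with 80% and 50% shown as a range. For N = 15, expected non-responders = 15(1 − p), and P(at least one) = 1 − p^15:
- p = 0.9: 1.5 expected; 1 − 0.9^15 = 0.79.
- p = 0.8: 3 expected; 1 − 0.8^15 = 0.96.
- p = 0.5: 7.5 expected; above 0.999.

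**(a) How far apart are the two means?** Assume a constant response rate with P(response by week 24) = p, seen only at weeks 4, 8, 12, 20 and 24. Then λ = −ln(1 − p)/24 and F(t) = 1 − exp(−λt), and P(first seen at a visit) is the step in F since the previous visit. The responder-only mean is m = Σ t·P(t)/p. The restricted mean is p·m + 24(1 − p), and the gap is (1 − p)(24 − m).

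For p = 0.9 the steps are 0.319, 0.217, 0.148, 0.169 and 0.047, so m = 9.30/0.9 = 10.33. The restricted mean is 0.9 × 10.33 + 0.1 × 24 = 11.70.

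| Response by week 24 | Responder-only mean (weeks) | Restricted mean (weeks) | Gap (weeks) | Median on visit grid |
|---|---|---|---|---|
| 90% | 10.3 | 11.7 | 1.4 | week 8 |
| 80% | 11.5 | 14.0 | 2.5 | week 12 |
| 50% | 13.3 | 18.6 | 5.4 | week 24 |

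From 90% to 50% response the responder-only mean moves 3 weeks, and the restricted mean moves 7.

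**(a) Same data, different rules (illustrative).** Ten of 15 respond: 3, 3, 2, 1 and 1 at weeks 4, 8, 12, 20 and 24.
- Responders only: 104/10 = 10.4 weeks.
- Non-responders set to 24: (104 + 5 × 24)/15 = 14.9.
- Non-responders set to 36: (104 + 5 × 36)/15 = 18.9.

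At the extreme, 2 of 15 responding at week 4 gives a responder-only mean of 4.0 weeks. Thirteen of 15 responding (2, 4, 4, 2 and 1 at the same visits) gives 152/13 = 11.7, so the far worse result looks faster.

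**(a) Which rule for early leavers (illustrative)?** Of 15, nine respond (two each at weeks 4, 8, 12 and 20, one at week 24), three complete without response, and three leave at week 8 for lack of effect. The responder-only mean is 112/9 = 12.4 weeks.
- Leavers censored at week 8: S(24) = 13/15 × 11/13 × 6/8 × 4/6 × 3/4 = 0.275, a response of 72.5%.
- Leavers kept to week 24: S(24) = 6/15 = 0.40, a response of 60%, which is the observed 9/15.

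The median is week 20 either way.

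**(a) Visit windows.** Sections 5.1.5 to 5.1.9 allow ±4, ±4, ±4, ±7 and ±4 days, each counted from the previous visit or injection. They sum to ±23 days, so a compliant week-24 visit can fall at (168 + 23)/7 = week 27.3. The horizon should therefore be the week-24 visit, not calendar week 24.

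**(b) Carriers.** Expected number = 15 × 0.125 = 1.9. P(0 or 1) = 0.875^15 + 15 × 0.125 × 0.875^14 = 0.135 + 0.289 = 0.42. Because familial cases may enter, take 10% to 25% as an assumed range: 1.5 to 3.75 carriers, with P(0 or 1) from 55% down to 8%.

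**(b) Behaviour of the t-test.**
- 0/1 versus 13/14: the difference is 0.929. The pooled variance is (13/14)/13 = 0.0714 and SE = √(0.0714 × (1 + 1/14)) = 0.277, so t = 3.36 on 13 df and p = 0.005. Fisher's exact test gives 2/15 = 0.13.
- 0/2 versus 13/13, or all 15 responding: within-group variance is zero, so there is no usable p-value. All 15 respond with probability 0.9^15 = 21% at 90% response.
- False-positive rate by full enumeration, common response 50% to 95%: 0.6–8.4% with 1 carrier, 2.3–5.4% with 2 and 4.4–8.8% with 3. Averaged over the carrier count at 12.5%, it is 2.3–5.4%.

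**The case against.** The strongest reply is that little turns on either item. This is a self-described pilot, no decision rests on them, and the primary paired t-test is unaffected. That stands, and it sets the importance.

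For (a), week 24 is the sensible reading of the horizon. At 90% response the gap of 1.4 weeks is shorter than the shortest 4-week visit interval. A reader might infer that the planned mean must flatter the drug. The documents do not support that: at 90% the visit-grid median (week 8) is earlier than the responder-only mean, and the larger gaps rest on assumed response rates. A reader might also infer that an early week-24 visit will be entered as week 24. Nothing says so; the analysis is stated in weeks, and the point is only that no rule is given. The planned graph could be a cumulative-response plot, but that is not stated, and no graph repairs the mean and SD.

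For (b), a reader might infer that the t-test inflates false positives. On average it does not. Nor is fragility peculiar to it: with 2 carriers, Fisher's test moves from p = 0.029 (0/2 versus 12/13) to 0.257 (1/2 versus 12/13). The carrier count is the main cause. Fisher's test is also no real remedy, since its average false-positive rate at 12.5% carriage is at most 0.64%. Section 7.2.3 already commits to reporting the proportions. What remains is an unsuitable p-value and a missing time point.

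**Conclusion.** Point (a) holds as a gap in a named secondary endpoint. Once one subject fails to reach PASI 50, the stated summary cannot be computed for the treated group without a rule that the plan lacks. Its size depends on response: about 1.4 weeks at 90%, 2.5 at 80% and 5.4 at 50%, under a constant response rate seen only at nominal visits. These response rates are assumptions; the documents give no PASI 50 rate for guselkumab in PRP. Importance is minor to moderate.

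Point (b) holds only as a minor exploratory item. The 12.5% applies to sporadic PRP, so 1.9 carriers is an expectation with wide spread. The case against the test is that single tables can mislead or yield no p-value, not that its long-run error is wrong.

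**What to change.** (a) In Section 7.2.2, replace the mean and SD with:

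> Time to first PASI 50 through the week-24 visit (including a week-24 visit within its window) will be shown as a Kaplan-Meier curve with median and 95% CI, together with n/N of all treated subjects reaching PASI 50. Subjects who complete the week-24 visit without PASI 50, and subjects who stop or withdraw for lack of effect, are kept as non-responders through the week-24 visit; other early leavers are censored at their last PASI. A sensitivity analysis censors all early leavers at their last PASI.

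Leaving for lack of effect is informative, so keeping those subjects as non-responders is the main analysis and censoring them is the sensitivity analysis.

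(b) In Section 7.2.3, drop the t-test. Report n/N with PASI 50 at the week-24 visit in each CARD14 group with exact 95% CIs, labelled descriptive.

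The cost is a few sentences of analysis text and one sensitivity analysis, with no new visits. Section 8.7.2 already has the reason for withdrawal documented, and Section 8.4.2.1 already has lack of effect recorded in the eCRF. The downsides are that the median moves in steps set by the visit schedule and may not be reached, and that the CARD14 comparison will be visibly uninformative: the exact 95% CI is 1% to 99% for 1/2 and 16% to 100% for 2/2.
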